Title: Randomized COmparison of Isolated Radial Artery ComPrEssioN versus Radial and Ipsilateral Ulnar Artery Compression in Achieving Radial Artery Patency: OPEN-Radial Trial

NCT Number: NCT04002791

Date: March 1, 2019

STUDY PROTOCOL AND STATISTICAL ANALYSIS PLAN

The study was conducted at a tertiary care center in India. The protocol was reviewed and approved by the local institutional review board.

Inclusion criteria: Patients referred for cardiac catheterization using TRA.

- Exclusion criteria: 1: Patients with a history of previous ipsilateral TRA.
 - 2: Warfarin anticoagulated patients or patients on novel oral anticoagulant compounds.
 - 3: Patients requiring continuous intravenous heparin infusion for any indication.
 - 4: Presence of plethysmographic waveform when both radial and ulnar arteries were occlusively compressed (suggestive of presumed interosseous artery related digital plethysmographic waveform).
 - 5: Absence of palpable ulnar pulse.
 - 6: Lack of informed consent.

Primary study endpoints:

The primary study endpoint was achievement of patent hemostasis, defined as presence of radial artery patency at 15 minutes after onset of hemostatic compression of radial artery, using plethysmographic technique as described below.

Secondary study endpoint:

The secondary study endpoint was RAO evaluated by plethysmographic technique, 1hour after the removal of hemostatic compression device was the secondary study endpoint.

All patients underwent Barbeau's test before the procedure, although TRA was performed if inclusion criteria were met. Reverse Barbeau test was also performed before the procedure, when the ipsilateral ulnar artery was transiently compressed in conjunction with radial artery compression, while plethysmographic waveform monitoring was in progress with the sensor placed on ipsilateral index finger. Total absence of waveform while both arteries were compressed was necessary for inclusion into the trial. Upon release of the radial artery, return of the waveform was considered evidence of patency of radial artery at baseline. Randomization scheme is depicted in the CONSORT diagram shown in Figure 1. Patients randomized to Group 1 received hemostasis post-procedure using TR Band (Terumo Interventional Systems, Japan), and Group 2, using VASOBand (VASOInnovations Inc., Los Angeles, California, USA).

Transradial Procedure:

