Categorical variables were expressed as proportions, and differences between the two groups were assessed using Chi-square test, or Pearson test as deemed appropriate. Numeric variables were assessed for normality of the distribution and were expressed as mean and standard deviation for normally distributed variables, and median as well as interquartile range for those without normal distribution. Parametric tests were used to compare differences between the two groups for normally distributed numeric variables, and nonparametric tests were used in those variables with a non-normal distribution. Paired t-test was performed to compare serial blood pressure observations. Binary logistic regression was performed to identify independent predictors of RAO. Mediation analysis was performed to identify potential mechanistic basis of the effect observed in the treatment (VASOBand) group.

Sample Size Calculation:

Based on the available literature, using the current standard of care TR Band, sample size was calculated for our primary study endpoint, achievement of patent hemostasis as defined above. We used an optimistic 80% patent hemostasis rate in the TR Band group in view of the high level of training of the research site in preventing RAO. The only published randomized trial using prophylactic ipsilateral ulnar artery compression during radial artery hemostatic compression has shown 96% achievement of patent hemostasis at 15 minutes after onset of compression. Using 80% rate of patent hemostasis in single-balloon band (TR Band) group and 95% rate of patent hemostasis in the dual-balloon band (VASOBand) group, a Chi-square model provided a sample size of 194 patients equally divided between two groups, necessary to achieve a 90% power with an alpha error of .05. Average incidence of RAO 1-hour after removal of

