hemostatic compression device, using the findings from recent trials reporting RAO rates at < 24 hours sampling^{5,9,12} was expected to occur in 11% of patients in TR-Band group and 1.5% in the experimental group, providing a sample size of a total of 250 patients in order to have a 90% chance of detecting a difference in the secondary end-point of RAO with an alpha=.05. It is important to note that RAO incidence is very dependent on time of evaluation after the procedure, data from recent studies mentioning the time point of RAO evaluation were used for sample size calculation. SPSS 26 (IBM Corporation, Armonk, NY) statistical software was used for the analyses.

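### Does giving 194 patients for patent hemostasis and 250 for RAO, without naming the enrolment target, leave the RAO comparison underpowered?

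*Combined protocol and SAP*

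**What the plan says.** In the combined protocol and SAP, the Sample Size Calculation section opens with the primary endpoint: "sample size was calculated for our primary study endpoint, achievement of patent hemostasis as defined above". With assumed rates of 80% (TR Band) and 95% (VASOBand), "a Chi-square model provided a sample size of 194 patients equally divided between two groups". The stated power for this total is 90% and the alpha is .05.

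The same paragraph then turns to RAO, the only named secondary endpoint, "expected to occur in 11% of patients in TR-Band group and 1.5% in the experimental group". This gives the second total: "providing a sample size of a total of 250 patients in order to have a 90% chance of detecting a difference". Alpha is again .05.

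No sentence in the available text says which total governs enrolment, whether alpha is one- or two-sided, or which formula lies behind 250. On the test, the Statistical Analysis section says that for categorical variables "differences between the two groups were assessed using Chi-square test, or Pearson test as deemed appropriate". On allocation, the text under the secondary endpoint says: "Randomization scheme is depicted in the CONSORT diagram shown in Figure 1". That figure is not reproduced in the available copy.

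**The concern.** Two totals with no stated choice between them make a reader ask which one applies. The section introduces the calculation as made for the primary endpoint, and sizing a trial on its primary endpoint is ordinary practice, so 194 is a possible reading. If 194 were the target, the primary power statement would hold but the RAO one would not. The chance of missing the assumed RAO difference would be about 17-20% by the exact uncorrected chi-square and the unpooled formula, where the plan speaks of 10%.

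RAO has its own power calculation and is the outcome of the planned logistic regression. Someone faced with a non-significant RAO comparison would want to know which power to attach to it.

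**Working it through.** **Inputs** (Sample Size Calculation): primary 80% v 95%; RAO 11% v 1.5%; alpha .05; power 90%; 194 split equally. **Assumptions:** two-sided test, equal split of the 250 as well, no dropout (none is stated).

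**1. Reproduce 194.** Unpooled normal formula, per arm: n = (z₁₋α/₂ + z₁₋β)² × [p₁(1−p₁) + p₂(1−p₂)] / (p₁−p₂)².

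- Two-sided: (1.960 + 1.2816)² × (0.80×0.20 + 0.95×0.05) / 0.15² = 10.508 × 0.2075 / 0.0225 = 96.9, so 97 per arm and 194 in total. This matches the plan.
- One-sided: 79.0 per arm, 158 in total. Of the two, only the two-sided version of this formula returns 194, so two-sided testing can be inferred.

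**2. Check 250 for RAO.** Totals needed for 90% power, two-sided, by method:

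| Method | Total |
|---|---|
| Arcsine | 228 |
| Exact power of uncorrected chi-square | 234 |
| Likelihood-ratio chi-square | 244 |
| Unpooled normal | 264 |
| Pooled normal | 270 |
| Continuity-corrected normal | 310 |

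The unpooled figure is 10.508 × (0.11×0.89 + 0.015×0.985) / 0.095² = 10.508 × 0.112675 / 0.009025 = 131.2, so 132 per arm. The plan's 250 lies inside the spread of standard methods, close to the likelihood-ratio value. None of the methods tried gives exactly 250.

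**3. RAO power at each total.** Unpooled: power = Φ(0.095 / √(0.112675/n) − 1.960).

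- n = 125 per arm: 0.095/0.03002 = 3.164, less 1.960 is 1.204, giving 88.6%.
- n = 97 per arm: 0.095/0.03408 = 2.787, less 1.960 is 0.827, giving 79.6%.

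The exact rows come from full enumeration of both binomial distributions.

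| Method | 250 | 194 |
|---|---|---|
| Exact, uncorrected chi-square | 91.9% | 82.7% |
| Likelihood-ratio chi-square | 90.8% | 82.5% |
| Unpooled normal | 88.6% | 79.6% |
| Pooled normal | 87.8% | 78.5% |
| Exact, continuity-corrected chi-square | 86.1% | 72.8% |
| Exact, Fisher's test | 86.1% | 74.4% |

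At 250 the stated 90% is approximately right. At 194 no method in the table reaches 90%.

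**4. Primary power at each total.**

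| Method | 250 | 194 |
|---|---|---|
| Exact, uncorrected chi-square | 96.4% | 91.3% |
| Unpooled normal | 95.7% | 90.0% |
| Pooled normal | 95.2% | 89.1% |
| Exact, continuity-corrected chi-square | 94.5% | 86.7% |

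**5. A limit on what 250 offers.** Whether 250 leaves room for missing RAO results depends on the method. The exact uncorrected chi-square reaches 90% at 234, which is 250 − 234 = 16 patients below the total. The unpooled formula needs 264, so by that measure 250 is 264 − 250 = 14 patients short. No general allowance for missing data should be read into it.

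**The case for a change.** The best case for a change runs as follows. The text really does not name a target, and its opening sentence leans towards the primary endpoint. Every method in the working loses between about 8 and 13 points of RAO power in moving from 250 to 194. The two totals do not come from one formula either: the unpooled calculation that returns 194 would ask for 264 for RAO. One or two sentences would settle the matter at no cost in patients.

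The facts stand, but they do not show a fault in the plan:

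- The 90% RAO power is attached to 250 in the same sentence. The 17-20% miss rate compares that statement with a scenario the plan never describes.
- The paragraph runs straight on from 194 to a larger total that covers both endpoints. When two endpoints are each sized and one total serves both, the larger is ordinarily the one that governs.
- The randomization scheme is referred to a CONSORT diagram that is missing from the copy. Such a diagram is an obvious place for the number randomized, so it cannot be established that the plan omits it.
- The difference between formulas moves RAO power at 250 by a few points around 90%. It does not make 250 wrong.
- A non-significant RAO result would be read from the number actually analysed and its confidence interval. The label on a planned total would not alter that reading.

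**Conclusion.** The concern does not call for a change. The plan contains no arithmetic error on this point: 194 reproduces exactly, and 250 is consistent with about 90% RAO power (86.1% to 91.9% in the table, according to the test and any continuity correction). Read with 250 as the target, both power statements are sound, and the primary endpoint has roughly 95-96% power (94.5% with continuity correction).

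What is unstated (the governing total, two-sided alpha, and the formula behind 250) is reporting detail that an analyst can fill sensibly from the text. RAO power would need restating only if 194 proved to be the real target: about 78-83% without continuity correction and about 73% with it. Even then RAO is secondary, and primary power at 194 is 90.0% by the formula that reproduces the plan's figure.

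This conclusion assumes two-sided testing, equal allocation, no dropout and the plan's own event rates.
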